11.1.2 Secondary Hypotheses

It is also hypothesized that:

- 1. A significantly greater percentage of TAU+SCT, relative to TAU, participants will provide a stimulant-free UDS result at the 3 and 6-month post-quit follow-up visits (see section 6.5.2.1).
- 2. TAU+SCT, relative to TAU, participants will have better drug-abuse outcomes during the active treatment phase including:
 - a significantly greater percentage of participants with drug-free weeks (see section 6.5.2.1);
 - significantly fewer stimulant-use and substance-use (i.e., alcohol and/or illicit drug use) days as assessed by the TLFB;
 - better compliance with substance-abuse treatment defined by a greater proportion of scheduled hours attended;
 - significantly greater decrease in ASI-Lite composite scores between baseline and end of treatment;
 - significantly greater decrease between baseline and end of treatment in sexual risky behavior as assessed by the sex risk scale of the RAB;
 - significantly greater reduction in cocaine/METH craving as measured by the BSCS from baseline through the end of the active treatment phase

- 3. TAU+SCT, relative to TAU, participants will have better drug-abuse outcomes at the 3- and 6-month post-quit follow-up visits including:
 - a significantly higher percentage of participants with drug-free urines at the 3- and 6-month followup visits (see section 6.5.2.1);
 - significantly fewer stimulant-use and substance-use (i.e., alcohol and/or illicit drug use) days as assessed by the TLFB at the 3- and 6-month follow-up visits (see section 6.5.2.1);
 - significantly lower ASI-Lite composite scores at the 3- and 6-month follow-up visits;
 - significantly lower RAB sex risk scale score at the 3- and 6-month follow-up visits;
 - significantly lower cocaine/METH craving as assessed by the BSCS at the 3- and 6-month follow-up visits
- 4. TAU+SCT, relative to TAU, participants will have better smoking outcomes during the active treatment phase including:
 - higher rates of point-prevalence abstinence (see section 6.5.2.2) at the week 10 assessment
 - higher rates of continuous smoking abstinence (see section 6.5.2.2) during post-quit days 15-42
 - a lower number of CPD during study weeks 4-9
- 5. TAU+SCT, relative to TAU, participants will have better smoking outcomes at the 3- and 6-month postquit follow-up visits including:
 - higher rates of point-prevalence abstinence (see section 6.5.2.2) at the 3- and 6-month follow-up visits

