11.3 Analysis Plan

Each primary and secondary efficacy outcome measure will be analyzed for the intent-to-treat (ITT) population. While there is every intention to be complete in describing the analyses to be performed, it is not possible to anticipate every contingency, and some adjustments may be required to meet constraints posed by the structure of the data. Constraints such as non-linearity, non-normality, etc. may lead to different but more appropriate approaches to analysis.

All statistical tests will be conducted at the 5% Type I error rate (two-sided). When multiple tests are conducted, the chance of finding a significant difference in one of the tests, when in fact no difference exists, is greater than the stated Type I error rate. The investigators are aware of the multiple testing issues and will interpret results with caution and use confidence intervals where possible.

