For a number of the remaining secondary outcomes, the effect of TAU+SCT, relative to TAU, is considered for both the active phase and follow-up phase. For these outcomes, a reference is made to controlling for baseline values. In the context of these analyses, the 'baseline value' for the active phase is the value of the outcome prior to randomization. If the analyses reveal a significant treatment effect during the active phase, then the 'baseline value' for the follow-up phase will be the outcome prior to randomization; this analysis will evaluate whether the effect observed during the active treatment phase is maintained through follow-up. If the analyses reveal no significant treatment effect during the active phase, then the 'baseline value' for the outcome measured at the end of the active phase; this analysis will evaluate whether a treatment effect becomes evident over a longer period of time (i.e., a "sleeper" effect).

5. The ASI- Lite

The seven areas of functioning measured by the ASI- Lite (medical status, employment status, drug use, alcohol use, family status, legal status, psychiatric status) will be assessed at baseline, the end of the active treatment phase and at the 3- and 6-month follow-up visits. These data will be analyzed using a repeated measures mixed model with group, time, time X group interaction and baseline values controlled as noted above. Significance of Group is declared if the joint effect of the Group and Group X time interaction (as defined by a change in log-likelihood) was significant (p<0.05). These 7 tests will be performed without adjustment for multiple testing.

6. Sexual Risky Behavior as assessed by the RAB

The sex risk scale of the RAB, which produces a score ranging from 0-28, will be assessed at baseline, the end of the active treatment phase and at the 3- and 6-month follow-up visits. The sex risk score data will be analyzed using a repeated measures mixed model with group, time, time X group interaction and baseline values controlled as noted above. Significance of Group is declared if the joint effect of the Group and Group X time interaction (as defined by a change in log-likelihood) is significant (p<0.05).

7. Cocaine/METH craving as assessed by the BSCS

The BSCS craving score, which ranges from 0-12, is assessed weekly during the active treatment phase and at the 3- and 6-month follow-up visits. These data will be analyzed using a repeated measures mixed model.

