11.4 Sample Size Estimate

The minimum sample size required to achieve 80% power using an alpha level of 0.05 (two-sided) and a 1:1 randomization ratio was computed based on a repeated measures study design that takes into account that the data are binary and can be correlated across repeated measurements (Rochon, 1998). We assumed a compound symmetry covariance structure to be conservative (correlation between 2 successive time points does not change over time), as well as a maximum correlation between any 2 time points of 0.65. The higher the assumed correlation between time points, referred to as phi, the less information that we gain from successive measurements, thus requiring a larger sample size. The assumption of 0.65 for the present study is based on the phi calculated for the stimulant UDS results from the subgroup of cocaine dependent participants in CTN-0009, a study that evaluated the impact of concurrently providing smoking-cessation treatment with substance-abuse treatment.

The probability of stimulant-free urines in the TAU group is another key assumption in determining sample size. A review of the stimulant UDS results for cocaine-dependent participants from three prior CTN studies, CTN-0009, CTN-0015 (Seeking Safety for women with PTSD and substance-use disorders), and CTN-0006 (Contingency management for stimulant abusers) produced probabilities ranging from 0.55 to 0.75, with the lower probabilities (i.e., 0.55) requiring larger sample sizes. Based on these prior studies, we assumed a probability of 0.6 for stimulant-free urines in the TAU group. A final key consideration in calculating sample size is the size of the group difference to be detected. The present study has been powered to detect the lower limit of a clinically meaningful effect. Specifically, this study will detect a group difference if the probability of stimulant-free urines in the TAU+SCT group is at least 0.7.

The sample size yielded from the assumptions outlined above is 528, with 264 in each treatment group. As described in section 11.6, an interim analysis to evaluate the accuracy of the assumptions made in calculating this sample size will be conducted, with an adjustment made to the sample size if needed.

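### For the ASI-Lite scales and the RAB sex-risk score, a non-significant week-10 test switches the follow-up covariate to the post-randomization week-10 value, so the model no longer estimates the difference stated in secondary hypothesis 3

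*Protocol*

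**What the plan says.** Protocol section 11.3.2 sets a rule for those secondary outcomes whose models refer to controlling for baseline. In the active phase, baseline is the pre-randomization value. For follow-up there are two branches:

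- "If the analyses reveal a significant treatment effect during the active phase, then the 'baseline value' for the follow-up phase will be the outcome prior", that is, the value taken before participants were randomized. The stated purpose is to see whether the effect is maintained.
- If there is "no significant treatment effect during the active phase, then the 'baseline value' for the outcome measured at the end of the active phase". The sentence is grammatically incomplete in the text available, but the purpose given after it (an effect that emerges late) makes the meaning plain: the week-10 score becomes the covariate.

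Only item 5 (ASI-Lite, seven scales) and item 6 (RAB sex risk) refer back to this rule. In Table 2, week 10 is the only active-phase assessment of either instrument.

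Section 11.1.2, hypothesis 3, puts the follow-up question without any condition on week 10: "significantly lower ASI-Lite composite scores at the 3- and 6-month follow-up visits", and likewise for the RAB sex-risk score. Secondary objective 3 in section 5.2 asks about longer-term impact in the same unconditional way.

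**The concern.** Three features combine.

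- The covariate is chosen by an earlier p-value, so week-10 results of p = 0.049 and p = 0.051 lead to different quantities at months 3 and 6.
- One of the two covariates is measured after randomization. For these instruments it is the very score that has just been tested for a treatment effect.
- Non-significance is treated as absence of effect, although a modest real effect will often miss 0.05 at week 10.

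A modest benefit that persists would then be understated in the trials where week 10 missed significance. A benefit that fades could be reported as a late disadvantage of TAU+SCT. Each of the eight scores can also fall into a different branch, so the follow-up results would not be comparable across scales.

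**Working it through.** **The plan's own figure.** The protocol gives no calculation for these follow-up analyses. Its only design figure is the 528 for the primary outcome, used here solely as the source of 264 per arm. The stated inputs are "we assumed a probability of 0.6 for stimulant-free urines in the TAU group", a TAU+SCT rate of 0.7, 80% power, two-sided 0.05 and "a maximum correlation between any 2 time points of 0.65". A two-proportion calculation with continuity correction gives 376 per arm. Ten weekly measures give a factor of (1 + 9 × 0.65)/10 = 0.685, so 376 × 0.685 ≈ 258 per arm, or 516 in total. That is within 3% of 528. Section 11.4 does not state the number of repeated measures; seven would give 528. Nothing below turns on this.

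**Inputs for the check**

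- Two-sided 5% tests (section 11.3) and 264 per arm (section 11.4).
- Correlation ρ between visits: not given for ASI-Lite or RAB. Values of 0.4 and 0.6 are assumed; 0.65 is borrowed from the stimulant urine results.
- True benefit of 0.15 SD: assumed.
- Simplification: unit variances, equal correlations, no dropout and ANCOVA at one follow-up visit, in place of the protocol's joint likelihood test of group and group-by-time over two visits.

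**Step 1: what each covariate estimates.** Let d10 and dF be the true benefits at week 10 and at follow-up. With the pre-randomization covariate the expected estimate is dF. With the week-10 covariate it is dF − ρ·d10.

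- Persisting effect of 0.15: 0.15(1 − ρ) = 0.090 at ρ = 0.4, 0.060 at 0.6 and 0.0525 at 0.65.
- Late effect only (d10 = 0, dF = 0.20): 0.20 with either covariate.
- Fading effect (d10 = 0.15, dF = 0, ρ = 0.65): 0 with the pre-randomization covariate, −0.65 × 0.15 = −0.0975 with the week-10 covariate.

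**Step 2: how often the branch is entered (persisting effect).** SE = √(2(1 − ρ²)/264), and the non-significant share is Φ(1.96 − 0.15/SE).

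- ρ = 0.6: SE = 0.0696, 0.15/SE = 2.154, Φ(−0.194) = 42%.
- ρ = 0.4: SE = 0.0798, 0.15/SE = 1.880, Φ(0.080) = 53%.

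**Step 3: mean estimates within the branch.** Trials in the branch are selected for a low week-10 result, so both covariates must be compared in the same trials. Let a = 1.96 − 0.15/SE and λ = φ(a)/Φ(a).

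- Pre-randomization covariate: 0.15 − [ρ/(1 + ρ)]·λ·SE.
- Week-10 covariate: 0.15(1 − ρ) + [ρ²/(1 + ρ)]·λ·SE.

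| ρ | λ | Pre-randomization | Week 10 |
|---|---|---|---|
| 0.6 | 0.925 | 0.15 − 0.375 × 0.925 × 0.0696 = 0.126 | 0.060 + 0.225 × 0.925 × 0.0696 = 0.074 |
| 0.4 | 0.748 | 0.15 − 0.286 × 0.748 × 0.0798 = 0.133 | 0.090 + 0.114 × 0.748 × 0.0798 = 0.097 |

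Simulation gives the same values to within about 0.003 SD. The like-for-like loss is about 0.05 SD at ρ = 0.6 and 0.036 SD at ρ = 0.4.

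**Step 4: power and errors (simulation, 264 per arm)**

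| Scenario | Protocol rule | Pre-randomization throughout |
|---|---|---|
| 0.15 SD persists, ρ = 0.6: power | 46–47% | 57% |
| 0.15 SD persists, ρ = 0.4: power | 38% | 46% |
| 0.15 SD fades to 0, ρ = 0.65: rejections in the wrong direction | 9–10% | 2.5–3% |
| Late effect only, 0.15 SD, ρ = 0.6: power | 58% | 58% |

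A variant that averages the two follow-up visits (ρ = 0.65) gives power of 62% against 77% for a persisting 0.15 SD effect, and wrong-direction rejections of 12.2% against 2.5% for a fading one. A late effect of 0.20 SD has 95% power either way. In that variant, type I error of the rule under the global null is about 5.3 to 5.7% over correlations from 0.4 to 0.8.

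**The case against.** The best defence is that both branches are prespecified and each has a stated purpose. The second branch openly looks for a late-emerging effect, and if week 10 truly shows nothing, adjusting for it does no damage. Only two secondary instruments are affected, the primary analysis is untouched, and section 11.3 already promises caution over multiple tests. All of that stands, and it limits the severity. It does not repair the mismatch: hypothesis 3 asks one question, the rule answers one of two, and a non-significant test does not establish that week 10 shows no effect. The switch also gains almost nothing, since the pre-randomization covariate detects a late effect equally well.

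Some stronger readings are tempting but are not supported:

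- *All follow-up outcomes are affected.* The models for follow-up urine results, TLFB days, craving, smoking abstinence and cigarettes per day do not refer to the rule.
- *The effect under test is removed.* Only a part of what was present at week 10 is subtracted; a late effect is kept in full.
- *The estimate falls from 0.150 to about 0.075 SD.* This compares selected trials with the unselected truth. The fair comparator in those trials is about 0.125 SD.
- *Participants without a week-10 score leave the intent-to-treat analysis.* That presumes complete-case handling of the covariate, which the protocol does not state and an analysis plan may settle. Section 7.6.1 also asks early discontinuers to return at week 10.

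**Conclusion.** The point holds for the seven ASI-Lite scales and the RAB sex-risk score. The p-value-dependent switch changes the estimand from an unconditional between-arm difference to one conditional on week-10 status. It attenuates a persisting effect by about ρ times that effect and can turn a faded benefit into an apparent harm. At an assumed 0.15 SD, overall power falls by about 8 to 11 percentage points for correlations of 0.4 to 0.6. These sizes rest on assumed effects and correlations and on a simplified test. The direction of the bias does not depend on the exact values, provided the scores are positively correlated over time and week 10 carries some effect. A reader might infer that false positives are inflated in general; under the global null they are not, to any material degree. Severity is moderate, because only secondary outcomes are involved.

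**What to change.** In section 11.3.2, replace the conditional rule with one instruction: every ASI-Lite and RAB model that tests an active-phase or follow-up hypothesis uses the pre-randomization value as the baseline covariate. If a late-emerging effect remains of interest, report the week-10-adjusted analysis for all eight scores, labelled exploratory, whatever the active-phase result. Rewrite the incomplete sentence at the same time.

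The change needs no new data and simplifies the programming. The cost is that the late-effect analysis is no longer the hypothesis test; the comparisons above show no meaningful loss of power to detect such an effect.

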6.0 STUDY DESIGN

6.1 Overview of Study Design

This is a 10-week, intent-to-treat, 2-group randomized controlled trial with follow-up visits at 3 and 6 months post-smoking quit date. As noted above, the present study will address a significant gap in the research literature by evaluating the impact of concurrent smoking-cessation treatment and substance-abuse treatment in stimulant-dependent individuals. Eligible participants will be randomized to the TAU+SCT or TAU arms. Participants randomized to the TAU+SCT arm will have a target quit smoking day at the end of study week 3. The primary outcome measure is whether (yes/no) a participant is stimulant-free during each week of the active treatment phase, as assessed by twice-weekly qualitative UDS (see section 6.5.1 for details). Secondary outcomes include drug-free UDS results, self-report of drug/alcohol use, substance-abuse treatment attendance, HIV risk behavior, point-prevalence abstinence for smoking, continuous abstinence for smoking during study weeks 6-9, breath carbon monoxide (CO) levels, and cigarettes per day (cpd). Safety measures will include vital signs, adverse events (AEs), and mood measures.

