8.10.2 Nicotine Inhaler

Study participants randomly assigned to the TAU+SCT condition will be prescribed 6-16 nicotine cartridges per day ad libitum starting with the smoking quit date (study day 20) through week 10. During week 10, participants will be provided with a 3 week taper in which a maximum of 12 cartridges per day is taken in the first week, a maximum of 8 cartridges per day is taken in the second week, and a maximum of 4 cartridges per day is taken in the third week.

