11.3.1 Primary Outcome

The primary hypothesis is that a significantly greater percentage of TAU+SCT, relative to TAU, participants will be stimulant-free during the weeks of the active treatment phase. For each participant, a stimulant-free week is defined as a week in which both urine samples test negative for stimulants and the participant self-reports no illicit stimulant use. A stimulant-positive week is defined as a week in which at least one urine sample tests positive for a stimulant or during which the participant self-reports illicit stimulant use. However, in the analysis of data from any clinical trial, strategies must be employed for handling missing data. In this trial, data for a week in which both urine samples are missing and the participant self-reports no illicit stimulant use will be treated as missing. For a week in which one stimulant-free UDS is produced, the second urine sample is missing, and the participant self-reports no illicit stimulant use or the self-report data are missing will be treated as negative (Table 6).

Data will be analyzed using a generalized linear mixed model (GLMM) for repeated-measures analysis (Brown and Prescott, 1999). Suppose Y represents the vector of observed response data, X and Z the fixed and random effects design matrices, and α and β be the vectors of fixed and random effects, respectively. Then, the GLMM model formulation assumes that

$$\mathrm{E}(\mathrm{Y}|\beta) = g^{-1}(\mathrm{X}\alpha + \mathrm{Z}\beta),$$

where $E(Y|\beta)$ is the expected value of Y conditional on the random effects vector, g^{-1} is the inverse link function, and $X\alpha + Z\beta$ is the linear predictor. The response variable Y will be modeled using the logit link function, i.e., $g(\mu) = \log(\mu / (1 - \mu))$. Fixed effects will include treatment group and week, while random effects will include site. SAS Proc GLIMMIX will be used to fit the model as follows:

proc glimmix; class site treatment; model Y = treatment week treatment*week / dist=binary link=logit covb solution; random intercept / subject=site; random _*residual_*/subject=patientid type=cs; run;

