11.3.2 Secondary Outcome

Several secondary analyses that will further elucidate the efficacy of TAU+SCT, compared to TAU, for treating smokers in outpatient substance-abuse treatment for cocaine or methamphetamine dependence have been included in this study. For all repeated measures mixed model and generalized linear mixed model (GLMM) analyses, the response variable will be modeled using the appropriate link function. The effect of the intervention on change in response from baseline will be addressed by the treatment by week interaction parameter. Each model will adjust for possible site differences by including site as a random effect. The SAS procedure MIXED will be used for continuous variables, while GLIMMIX will be used for binary data. Before modeling is commenced, assumptions of linearity and covariance structure will be examined.

1. Stimulant-free/Drug-free UDS

GLMM analyses will be conducted to compare the percentage of TAU+SCT, relative to TAU, participants who have stimulant-free and drug-free UDS at the 3- and 6-month follow-up visits. Imputation methods used for the primary endpoint analysis will also be used for the 3- and 6-month models.

2. Drug-free Weeks

GLMM analysis will be conducted to compare the percentage of TAU+SCT, relative to TAU, participants who have drug-free weeks during the active treatment phase. Imputation methods used for the primary endpoint analysis will also be used for the analysis of drug-free weeks.

3. Stimulant-use and Substance-use Days

A repeated measures mixed model analysis will be conducted to compare the stimulant-use and substanceuse days reported during the active treatment phase as a function of treatment group. A mixed model analysis will also be conducted to compare the stimulant-use and substance-use days reported for the 28 days prior to the 3 and 6-month follow-up visits as a function of treatment group.

4. Ratio of treatment hours attended to hours scheduled

The ratio of the number of outpatient (including intensive outpatient) substance-abuse treatment hours attended to the number of hours scheduled during the active treatment phase will be analyzed using a GLMM

analysis with the log of the number of scheduled hours and the type of patient (intensive outpatient or outpatient) as covariates.

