8. Smoking Point-Prevalence Abstinence

GLMM analyses including site and treatment group will be used to model rates of achieving point prevalence abstinence as assessed at the week 10 visit of the active treatment phase and at the 3- and 6- month follow-up visits.

9. Continuous Smoking Abstinence

GLMM analyses including site and treatment group will be used to model rates of achieving continuous smoking abstinence during post-quit days 15-42.

10. Cigarettes per Day (CPD)

Given the smoking quit date's likely substantial impact on CPD, analyses for CPD during the active treatment phase will be conducted for the pre-quit and post-quit phases as well as for the entire treatment phase, with the treatment x week interaction effect for study weeks 4-9 being the effect of interest. A

repeated measures mixed model analysis will be conducted to compare the CPD reported for the 28 days prior to the 3 and 6-month follow-up visits as a function of treatment group.

11. Participants with Continuous Smoking Abstinence

The primary outcome analysis will be modified to compare the percentage of participants who achieve continuous smoking abstinence, relative to those who do not, on stimulant-free weeks during study weeks 4-10 of the active treatment phase. In addition, GLMM analyses will also be conducted to compare the percentage of participants who achieve continuous smoking abstinence, relative to those who do not, on stimulant-free UDS at the 3- and 6-month follow-up visits.

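### Active-phase cigarettes per day is hypothesised as a lower level in weeks 4-9 but tested by an interaction within those post-quit weeks, which can miss or misstate a real reduction

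*Protocol*

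**What the plan says.** The hypothesis for active-phase CPD (Protocol section 11.1.2, item 4) is that TAU+SCT participants will show "a lower number of CPD during study weeks 4-9". That is a statement about level.

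The analysis (section 11.3.2, item 10) starts from the expectation of a sharp change at quitting: "Given the smoking quit date's likely substantial impact on CPD". It plans pre-quit, post-quit and whole-phase analyses, "with the treatment x week interaction effect for study weeks 4-9 being the effect of interest".

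On timing, section 6.1 says that TAU+SCT participants "will have a target quit smoking day at the end of study week 3". Section 8.10.2 prescribes the inhaler "starting with the smoking quit date (study day 20) through week 10".

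The general rule for the secondary repeated-measures models (opening of section 11.3.2) is: "The effect of the intervention on change in response from baseline will be addressed by the treatment by week interaction parameter".

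The only model written out as code is the one for the primary outcome (section 11.3.1): "proc glimmix; class site treatment; model Y = treatment week treatment*week". Week is not a class variable there, so it enters as a linear trend. For the ASI-Lite and the RAB sex risk score the protocol uses a different test, with baseline controlled: "Significance of Group is declared if the joint effect of the Group and Group X time interaction". No such test is given for CPD.

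**The concern.** The hypothesis and the effect chosen to judge it are different quantities. A lower number of cigarettes in weeks 4-9 is a gap between two curves. A treatment-by-week interaction within weeks 4-9 is a change in that gap over those weeks. The protocol expects the large fall in smoking at the quit date, before the window opens. The general rule says that the interaction carries change from baseline, but a window of weeks 4-9 holds no baseline or pre-quit week from which to measure change.

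At stake is the conclusion on one of the three active-phase smoking hypotheses under secondary objective 4. A treatment that clearly lowers CPD could be reported as having no effect on it, or as doing worse. Replacing the contrast after the data are seen would look data-driven.

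**Working it through.** The protocol states no effect size, SD or power for CPD, so there is no figure to reproduce. The check sets the two quantities side by side under stated profiles.

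**Timing.** If week 1 starts on study day 1, week 3 is days 15-21 and week 4 starts on day 22. The quit date is day 20. All of weeks 4-9 follow it.

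**Inputs from the protocol.** 264 per arm (section 11.4); two-sided 5% tests (section 11.3).

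**Assumptions.** The CPD means in the table; SD 8 (range 6-10); compound symmetry with within-person correlation r = 0.65 (range 0.5-0.8), borrowed from the stimulant urine assumption in section 11.4; complete data.

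**Formulas.** Let d_w be the TAU+SCT minus TAU mean in week w. Weeks 4-9 have mean 6.5, and the sum of (w - 6.5)² is 17.5.

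- Interaction (difference in slope) = Σ(w - 6.5)·d_w / 17.5. Its SE = √[(2/264)·SD²·(1 - r)/17.5] = √[(2/264)·64·0.35/17.5] = 0.098 CPD per week.
- Level = mean of d_w. Its SE = √[(2/264)·SD²·(1 + 5r)/6] = √[(2/264)·64·4.25/6] = 0.59 CPD.

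| Profile, weeks 4-9 | Level difference (z) | Interaction per week (z) | Interaction test rejects |
|---|---|---|---|
| A. TAU+SCT 5, TAU 13 throughout | -8.0 (-13.7) | 0 (0) | 5%, the error rate only |
| B. TAU+SCT drifts 4 to 8, TAU 13 | -7.0 (-11.9) | +0.80 (+8.1) | about 100%, wrong sign |
| C. TAU+SCT drifts 5 to 6, TAU 13 | -7.5 (-12.8) | +0.20 (+2.0) | about 53%, wrong sign |
| D. TAU+SCT 5, TAU drifts 13 to 12 | -7.5 (-12.8) | +0.20 (+2.0) | about 53%, wrong sign |
| E. Late quitting: TAU+SCT 7 to 5, TAU 13 | -7.0 (-11.9) | -0.40 (-4.1) | about 98%, correct sign |

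Varying SD over 6-10 at r = 0.65, and r over 0.5-0.8 at SD 8, moves the wrong-sign rate in C and D between 37% and 77%. The level contrast has about 100% power and the correct sign in every case tried. Simulation of 2,000 trials each for A, B, C and E agreed (for C, 52.6% wrong-sign rejections).

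**Does categorical week help?** Not within weeks 4-9. In profile A every d_w is -8, so every difference between weeks is -8 - (-8) = 0.

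**What restricting the window removes.** Take TAU+SCT means of 15, 15, 14 in weeks 1-3 and 5 in weeks 4-10, and TAU means of 15 in weeks 1-3 and 13 in weeks 4-10. The post-quit arms are parallel, as in A. The weeks 1-10 interaction is [(3 - 5.5)(-1) + (-8)(10.5)]/82.5 = -81.5/82.5 = -0.99 per week, with SE 0.045 and z -21.8. Once pre-quit weeks are included, the effect is visible.

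**The case against.** **Late quitting is part of the design.** Section 10.0 lets participants start earning prize draws in any week in which they give a qualifying sample, expressly to keep late quitters trying. Section 6.5.2.2 allows a two-week grace period after the quit date, roughly weeks 4 and 5. CPD may still be falling inside the window, and profile E shows that the interaction then has the correct sign. This stands. A reader might infer that the slope measures only relapse or is bound to mislead; the documents do not support that.

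**Another model may be meant.** Item 10 attaches the interaction to a set of analyses that includes the entire phase, and the general rule speaks of change from baseline. In a whole-phase model with categorical week and a pre-quit reference, each weeks 4-9 interaction term would be a change from that reference: with the means above, (5 - 13) - (15 - 15) = -8. That would capture the drop. The code with linear week is for the binary primary outcome, and section 11.3.2 says linearity will be examined before modelling. But this model is stated nowhere, and if it is intended the sentence still needs rewriting to say so.

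**Other smoking results are safe.** A reader might infer that secondary objective 4 as a whole would be misreported. It would not: week-10 point-prevalence abstinence and continuous abstinence are modelled directly by treatment group, as is CPD for the 28 days before each follow-up visit. A whole-phase CPD analysis is also planned, though it is not the one named as of interest.

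**Conclusion.** The mismatch between hypothesis and test holds, in a conditional form. An interaction estimated within weeks 4-9 is zero for any constant between-arm difference, has the wrong sign under partial relapse in TAU+SCT, and the right sign under continued late quitting. It can therefore miss or misstate a real reduction in active-phase CPD.

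The zero in profile A is algebra and needs no assumption about SD or correlation. The z values and rejection rates rest entirely on assumed means, SD and correlation. A reader might take wrong-sign significance as the expected result. The documents do not support that: they give no CPD figures, and in the mild-drift profiles it occurs in roughly half of trials (37% to 77%).

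The point touches one secondary outcome. It should be fixed, but it does not bear on the primary outcome, the sample size or safety.

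**What to change.** In section 11.3.2 item 10, make the effect of interest the treatment difference in mean CPD averaged over study weeks 4-9 (a least-squares-mean contrast from the repeated-measures model), adjusted for pre-randomization CPD. Keep the weeks 4-9 treatment-by-week interaction as a secondary description of relapse or late quitting.

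A workable alternative is the joint group and group-by-time test already used for the ASI-Lite and RAB, with baseline controlled and the direction read from the mean difference. If a whole-phase model with a pre-quit reference was intended, state the coding of week and the reference.

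The cost is one sentence and one contrast. No new data are needed: the Timeline Follow-back is already scheduled at screening/baseline and twice weekly in Table 2. The change should be made before outcome data are compared by arm.
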